## **24. Provisions for Research Related Harm/Injury**

### **Non-Significant Risk**

The Ekso GT is a non-significant risk device in the context of the WISE trial. The device is 510(k) cleared by the FDA (K161443) for Individuals with spinal cord injuries at levels T4 to L5 (upper extremity motor function of at least 4/5 in both arms), and individuals with spinal cord injuries at levels of C7 to T3 (ASIA D with upper extremity motor function of at least 4/5 in both arms). Where injuries at a higher level than currently cleared by the FDA are included (C1 to T3), the inclusion criteria is in line with the Ekso GT intended use in the EU per the CE certification (UL as notified body), which has been in effect since 2013 without any serious adverse events. Users must meet functional requirements, including but not limited to sufficient upper body strength to control a walking aid such as a walker, crutches, or a cane. Users must also obtain physician clearance of health status prior to inclusion. Further, the Ekso GT has a number of safeguards to minimize risk to patients and therapists, as outlined below, and is used under the supervision of a physical therapist who has successfully completed the level 2 Ekso Bionics training program.

The Ekso GT is equipped with mechanical hard stops at the limits of healthy subject ranges of motion to prevent powering the joint of the user to a position that the joint cannot reach. The ranges of these joints were selected to provide for necessary functions such as standing, sitting, and walking. Redundant position sensing on all of the actuated joints ensures that the motors are always controlled using reliable sensor information. In addition, the device has numerous sensor, motor, and software monitoring systems. If an abnormality is detected (i.e. excess joint speed or force, or if redundant sensors do not agree) the device enters a safe mode, which prevents continued walking and enables the physical therapist to safely remove the patient. The device is also equipped with fail-safe brakes on the actuated knee joints, such that if the device loses power or is shut down (as in safe mode) for any reason the knees will continue to support the patient. Finally, an emergency disable button is available to instantly shut down the device for any reason. This is implemented via hardware, so it is effective even during a software malfunction.

## **25. Potential Benefits of Participation**

Community-dwelling participants often exhaust their medical insurance coverage for physical rehabilitation and retreat from community involvement unless they are presented with an opportunity to participate in a study or are willing to pay out of pocket for training sessions. This study affords those individuals an opportunity to undergo training when they may not have otherwise done so. Participants may also make improvements physiologically, psychologically, as well as in physical performance, specifically walking. This study is set up to benefit all groups though equal benefits cannot be ensured.

## **26. Monitoring Procedures**

Study monitoring will be performed in accordance with sponsor procedures, or those approved by sponsor. The Clinical department will have overall management responsibility for this study. In addition the Clinical department will direct regional monitoring staff, and may serve as clinical study monitors, study administrators, and/or have oversight responsibility for data review and data integrity. Ekso Bionics, Inc. may engage the services of one or more qualified organizations or individuals to perform monitoring and data management functions, and provide participating sites with relevant contact information, as necessary. Study monitors may change periodically over the course of this study. All monitors will be qualified to perform their assigned responsibilities, and participating investigators/site personnel will be notified of any changes as they occur.

On-site monitoring of all participating sites will be frequent enough to assure continued acceptability of the

data by assessing site compliance with the study protocol, adherence to data collection procedures, and maintenance of study records. Scheduled site visits may include, but are not limited to, the following:

- Site initiation visit: An initiation visit will be conducted by clinical personnel to review this study protocol, review the progression strategy for both groups, undergo an evaluation of the site's training status and refresh as required, and discuss source document/ CRF completion and transmittal procedures. Alternatively, a meeting may be conducted for several sites at a common location.
- Interim monitoring site visit: On-site monitoring visits will be conducted at all sites to assess the progress of the study and identify any concerns that result from review of the study records, study management documents, or Participant informed consent documents. To assure the integrity of the data, a representative number of individual Participant records and other supporting source documents will be compared to CRFs completed at the site to determine that:
  - The study protocol is being followed, and only eligible Participants are being enrolled; variances, if they occur, are recorded and reported as appropriate
  - Informed consent is properly documented
  - Adverse Events are being reported appropriately
  - Information recorded on CRFs is complete, accurate and legible
  - Missed follow-up visits and multiple attempts to contact Participant are properly documented
  - Participants failing to complete the clinical study and the reason for failure are properly recorded
- Final monitoring/Close-out site visit: At the close of the study, appropriately trained personnel appointed by the Sponsor will perform a close-out process via the telephone or on-site. The purpose of this visit is to collect all outstanding study data documents, ensure that the investigator's files are accurate and complete, review record retention requirements, provide for appropriate disposition of any remaining supplies, and ensure that all applicable requirements are met for the study. The observations and actions made during this procedure will be documented and communicated to the investigator.

## **27. Publication**

Manuscripts, abstracts, posters, or other informational materials may be presented at scientific meetings, or published in professional journals. The Sponsor reserves the right to publish the results of the run-in group and/or primary endpoint analysis results on the minimum sample size needed in a single publication. Longer-term, qualitative and quantitative analysis may be reported in a separate publication. This study will be listed on clinical trials.gov. Therefore, results will be published per FDA requirements.

## 29. Appendix A – Description of Standardized Measures and Assessments

### International SCI Basic Data Sets and Modified Basic Data Sets

The purpose of the International SCI Basic Data Sets is to promote data collection in a uniform manner and documented in a standard format, with precise instructions for each question. The International SCI Basic Data Sets used for the purposes of this study include:

1. Medical History (study specific minor modifications/deletions were made to the exploratory data set) and Demographics (core data set).
2. The International SCI Quality of Life (QOL) Basic Data Set will be used to collect data on quality of life. The International SCI (QOL) Basic data set collects information on three variables: ratings of satisfaction with general quality of life, satisfaction with general quality of life, satisfaction with physical health, and satisfaction with psychological health which are rated on a scale of 1-10.
3. The International SCI Pain Basic Data Set collects information on up to three pain problems, their location, severity, and temporal pattern, as well as impact in daily activities and well-being.
4. Bowel function data will be collected using the Modified International SCI Bowel Function Data Set, which contains 12 items to assess the impact of neurogenic bowel dysfunction ranging from bowel dysfunction unrelated to SCI, surgical procedures related to bowel function, awareness of the need to defecate, defecation method and frequency, incontinence and the use medications impacting bowel function. Reliability has been assessed for this data set.
5. The Modified International SCI Lower Urinary Tract Basic Data Set will be collected to assess lower urinary tract function. The following data will be collected: urinary tract impairment unrelated to spinal cord lesion, awareness of the need to empty the bladder, bladder emptying, average number of voluntary bladder emptyings per day during the last week, incontinence, collecting appliances for urinary incontinence, any drugs for the urinary tract, surgical procedures on the urinary tract and any change in urinary symptoms.

### The Medical Research Council Manual Muscle Test (MMT) Scale (as used in the ISNCSCI exam)

The manual muscle test is a standardized assessment to measure muscle strength. Score range 0-5, minimum 0, and maximum 5/5. For the purpose of this study, the Medical Research Council MMT Scale as used in the ISNCSCI exam will be used.

### Modified Ashworth Scale

As summarized in the National Institute of Neurological Disorders and Stroke Common Data Elements (NINDS CDE) for multiple sclerosis, the Ashworth scale is a widely used method of measuring spasticity, due in a large part to the simplicity and reproducible method. Scores range from 0---5, plus a 1+ scoring category to indicate resistance through less than half of the movement. A score of 0 indicates no resistance and 4 indicates rigidity. Assessment techniques for the MAS must be standardized. Some critics question the validity of the scale and Modified Ashworth Scale in measuring spasticity. It may be a description of resistance to passive movement. Therefore, it measures only one aspect of spasticity, and is not a comprehensive assessment. Administration time is approximately 5 minutes for the six muscle groups tested in this study.

### **Spinal Cord Assessment Tool for Spastic Reflexes (SCATS)**

The Spinal Cord Assessment Tool for Spastic Reflexes (SCATS) assesses three types of spastic motor behaviors in SCI patients - clonus, flexor spasms, and extensor spasms. SCATS Clonus scale uses passive dorsiflexion to assess clonus. SCATS flexor spasm is assessed with a pinprick to the medial arch with the knee and hip fully extended. SCATS extensor spasms are assessed by extending the hip and knee joints from a start position of 90 to 110 degrees of hip and knee flexion. Administration time is usually 5 to 10 minutes.

### **Berg Balance Scale (BBS)**

The Berg Balance Scale is a 14-item objective measure designed to assess static and dynamic balance and in adult populations. Scores range from 0-56, and cut-off scores exist for inferring a participant's categorical fall risk. This test takes an average of 15 minutes to administer. Low-level participants may complete the test in a couple of minutes, if they cannot perform any of the 12 tasks done in standing. However, high-level participants may require up to 30 minutes, because they will be able to attempt all 14 tasks, and may require rest breaks.

### **International Standards for Neurological Classification of SCI (ISNCSCI)**

The International Standards for the Classification of Spinal Cord Injury (ISNCSCI) were developed by the American Spinal Injury Association in 1982 in order to promote common definitions of neurological levels and the extent of complete injuries in patients with SCI and to achieve more consistent and reliable data among centers participating in the National Spinal Cord Injury Database. The Standards have been revised, with the last revision occurring in 2011 with an accompanying article to clarify the changes. The ASIA Standards are the most commonly used neurological examination for classifying patients with SCI for both clinical and research purposes. Since the last publication of a reference manual an electronic on line training program was developed, the International Standards Training e-Learning Program (InSTeP).

The neurological examination consists of both a motor and sensory exam that have been standardized to promote consistency. The ISNCSCI exam consists of the following:

1. Motor examination: 10 key muscles are tested in each half of the body. Each muscle is graded from 0 to 5 and then the total score is calculated, the maximum being 100.
2. Sensory examination: 28 key regions are tested in each half of the body for pinprick and light touch sensations. Each region is given a score of 0 (absent), 1 (impaired), 2 (normal) or NT (not testable). The total score is then calculated with a maximum of 112.

In addition, based on the data collected from the motor and sensory exams, neurological level, completeness of neurological loss, the zone of partial preservation and the ASIA Impairment Scale (AIS) can be determined.

### **10 Meter Walk Test**

The objective of this test is to assess walking speed in meters per second over a short duration. The individual is instructed to walk a distance of 14 meters. The middle 10 meters is timed to allow 2 meters for acceleration at the beginning and deceleration at the end of the walk. The distance covered is divided by the time it took the individual to walk that distance. Data will be collected using both baseline and current braces/devices at both self-selected and fast gait speeds during the 6, 12, and 24 week (midpoint, endpoint, and follow-up) evaluations. Data using current devices and no braces at self-selected speed will be collected every 3rd session as an indicator of incremental neurological recovery.

### **GAITRite Pressure Map**

The GAITRite pressure map is an optional test that may be used during the 10MWT, if the site has access to it, at any 10MWT evaluation timepoint. This pressure map will digitally record the placement and pressure of the participant's footprints as they walk over it during the 10MWT. From this data, it will calculate temporospatial gait parameters, such as swing and stance times, lengths, widths, etc. If used, the GAITRite mat will be placed to begin at the 2 meter mark on the 10MWT pathway. Clear packing tape will be used to tape the ends to the floor to reduce the risk of any walking device being caught in its edges and disrupting the flow of the step pattern. This should also reduce the participant's tendency to slow down or pause at the edge. Because the GAITRite is not placed in the middle of the pathway, each trial of the 10MWT will need to start from the same place.

### **Timed Up and Go (TUG)**

As summarized in the National Institute of Neurological Disorders and Stroke Common Data Elements (NINDS CDE) for multiple sclerosis, the original purpose of this test was to test basic mobility skills of frail elderly patients. The test has been used in other populations, including individuals with SCI. The original Get Up and Go Test used an ordinal scoring system based on the observer's assessment of the patient's risk of falling. The participant wears their regular footwear and uses their customary walking aid (none, cane, walker). No physical assistance is given. The subject walks through the test once before being timed in order to become familiar with the test. Either a stopwatch or a wristwatch with a second hand can be used to time the trial. The timed "Up and Go" test measures, in seconds, the time taken by an individual to stand up from a standard arm chair with approximate seat height of 46 cm [18in], arm height 65 cm [25.6 in]), walk a distance of 3 meters (118 inches, approximately 10 feet), turn, walk back to the chair, and sit down. Patients are timed (in seconds) when performing the TUG: from sitting in a chair, stand up, walk 3 meters, turn around, walk back, and sit down. The time taken to complete the task is strongly correlated to level of functional mobility, (i.e. the more time taken, the more dependent in activities of daily living) but will take less than 3 minutes. Psychometric properties for use in SCI have been assessed in multiple publications including but not limited to Ponchumak, et al., and van Hedel, et al.

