### **4. Study Endpoints**

The primary and secondary endpoints are as follows:

The primary endpoint is the mean increase in gait speed demonstrated during the 10MWT after 12 weeks/ 36 sessions of training and compared between groups. Both self-selected and fast speeds will be performed on the 10MWT, with the fast speed taking precedent.

The secondary endpoints of Participant outcomes related to physical performance, physiology, quality of life, and safety are to be measured at week 6/following 18 sessions (midpoint), week 12/following 36 sessions (primary endpoint), and week 24/3 months after the last session (follow-up) (unless otherwise indicated) and compared between groups.

By category, these are the following:

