#### PHYSICAL PERFORMANCE OUTCOMES

10MWT for both self-selected and fast gait speed

Number of participants who achieve the Minimal Clinically Important Difference (MCID) of 0.15 m/s during the 10MWT

Number of participants who transition from exercise or household ambulation (defined as self-selected walking speed of < 0.44 meters/second) to limited community or full community ambulation ( $\geq 0.44$  meter/second) during the self-selected 10MWT

Time point of recovery at which participants reach the MCID and/or community ambulation speeds of  $\geq 0.44$  meters/second

6MWT for endurance

Timed Up and Go (TUG) for balance during sit-to-stand, walking, turning, and stand-to-sit

WISCI-II score for need of assistance and devices

SCI-FAI for observational gait quality

GAITRite for temporospatial gait parameters and symmetry (if site has access to this device)

SCIM-III, mobility subscale for ability to perform transfers and walking different distances

Berg Balance Scale for measurement of static balance and dynamic sitting and standing balance.

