## 7. Inclusion/Exclusion Criteria

### *Inclusion criteria:*

1. Motor incomplete paraplegia or tetraplegia, chronic ( $\geq 1$  year after the injury). Non-traumatic SCI injuries can be included, given they are neurologically stable conditions for 12 months (e.g. tumor, transverse myelitis, but NOT Guilliane-Barré)
2. NLI C1- approximately T10 (inclusive, for upper motor neuron injuries only), as determined by the International Standards for Neurological Classification of SCI (ISNCSCI)
3. Sufficient diaphragmatic strength such that respiration is not compromised with exercise.
4. Sufficient upper extremity strength to use a front wheeled walker by manual muscle testing (minimum triceps strength bilaterally of 3/5, shoulder abduction and flexion/extension 4/5)
- 5.. AIS-C SCI & AIS-D SCI, as determined by the International Standards for Neurological Classification of SCI (ISNCSCI)
- 6.. Ambulates at a self-selected speed of <0.44 meters/second with or without physical assistance and assistance device
7. Able to advance at least one leg forward (volitionally with lower extremity movement ( not as a result of trunk movement or spasticity) while using parallel bars, walker or crutches, with or without braces, and up to 2 people to assist with safety and balance only. Stepping is to be performed by the patient (without PT assistance at the lower extremities and no BWS).

8. 18 – 75 yrs, inclusive
9. No current or history of other neurological conditions
10. Screened and cleared by a physician
11. Involved in standing program or must be able to tolerate at least 15 min upright without signs or symptoms of orthostatic hypotension
12. Weigh 220 pounds (100kg) or less
13. Be able to fit into the Ekso device
14. Between approximately 5'0" and 6'4" tall
15. Standing hip width of approximately 18" or less
16. Have near normal range of motion in hips, knees and ankles

*Exclusion criteria:*

1. AIS-A SCI or AIS-B SCI
2. Lower motor neuron injuries, as shown by absent reflexes during bilateral quadriceps and Achilles tendon taps

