3. < 3 months since previous intensive gait training regimen, FES cycling program, and lower extremity botox injections. The gait training regimen is meant to be formal gait training with feedback for progression of walking (i.e. PT sessions). Participant may have a regular home exercise program and/or a walking exercise program with a companion/ trainer for safety, but not for verbal or tactile cues or feedback regarding gait in the 3 months before initiating the protocol. If participant has a home exercise program and/or a walking exercise program, these programs (except FES cycling) should be continued without changes throughout the protocol. Electrical stimulation devices used regularly for foot drop during ambulation should be considered a brace and should continue to be used as usual throughout the protocol. Upper extremity botox injections are permissible before and during the protocol. One or two PT sessions are allowed to obtain a new brace or progress bracing and check for fit and safety, but no sustained gait training should occur.
4. Already walking at self-selected ambulation speeds of at least 0.44 meter/second with or without assistance
5. Currently involved in another intervention study
6. Concurrent neurological disease
7. Hip flexion contracture greater than ~17°
8. Knee flexion contracture greater than 12°
9. Unable to achieve neutral ankle dorsiflexion with passive stretch (neutral with max 12° knee flexion)
10. Leg length discrepancy

- a. Greater than 0.5" for upper leg
- b. Greater than 0.75" for lower leg

11. Spinal instability
12. Unresolved deep vein thrombosis
13. Uncontrolled autonomic dysreflexia
14. Severe muscular or skeletal pain
15. Spasticity that prevents joint motion (severe stiffness or rigidity,) where both legs have a MAS score of 3 or higher for half or more of their proximal lower extremity muscles; proximal muscles include hip flexors/extensors/adductors and knee flexors/extensors.
16. Open skin ulcerations on buttocks or other body surfaces in contact with exoskeleton or harness
17. Pregnancy
18. Cognitive impairments – unable to follow 2 steps commands and communicate for pain or to stop session
19. Shoulder extension ROM < 50° excludes crutches during sit to stand or vice versa. (Walking with crutches permitted.)
20. Participant requires the assistance of more than one therapist to transfer safely.

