## **18.1 Handling of Dropouts, Treatment Rescues and Missing Data**

Values for missing data will not be imputed, but exploratory analyses may be performed using the last real assessment for that patient (LOCF).

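### The Timed Up and Go allows no physical help, but eligible participants may need it, and the plan has no rule for a participant who attends and cannot do the test

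*Protocol*

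**What the plan says.** Protocol section 4 lists the test among the physical performance outcomes: "Timed Up and Go (TUG) for balance during sit-to-stand, walking, turning, and stand-to-sit". Secondary endpoints are measured at weeks 6, 12 and 24 ("unless otherwise indicated) and compared between groups"). Table 2 limits the week 24 visit to Groups 1 and 2.

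Appendix A scores the TUG only as seconds to rise, walk 3 m, turn, return and sit. On help during the test it says: "No physical assistance is given". A footnote to Table 2 requires the baseline device and braces at every TUG. No entry for a failed attempt, ceiling time or record of assistance is described. The 6-minute walk, by contrast, has its level of assistance recorded.

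Three criteria in section 7 bear on who can do this test:

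- Inclusion 6 sets a speed limit for people walking "with or without physical assistance and assistance device".
- Inclusion 7 permits "up to 2 people to assist with safety and balance only" while the participant steps.
- Exclusion 20 reads "Participant requires the assistance of more than one therapist to transfer safely", so a person who needs one therapist to transfer remains eligible.

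Protocol section 17.1 bases the analysis on all available data under intent-to-treat. Section 18.1 says "Values for missing data will not be imputed" and allows last observation carried forward (LOCF) only as an exploratory analysis. SAP section 1.1 plans analysis of variance or covariance for continuous outcomes, with rank analysis of variance if normality fails. SAP section 1.7 deals with people who discontinue, not with a test that cannot be done at an attended visit.

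**The concern.** The test begins and ends with a chair transfer and must be done unaided, while the entry criteria admit people who may need help to transfer or to walk. For such a person the result is not unknown: being unable is the worst outcome the test can give. A scale in seconds has no place for it, and the missing-data rule then removes it from the analysis.

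What is at stake is who the TUG comparison describes and whether it keeps to intent-to-treat. A participant who moves from unable to able may have made one of the larger functional gains in the trial and would have no change score. One who moves from able to unable would be removed because of that loss.

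**Working it through.** **Inputs.** The documents give no figure for the TUG: no SD, effect, sample size or share unable. The evaluable group sizes of 38, 38 and 19 come from protocol section 17.4, where they were derived for the gait-speed endpoint, and serve here only as denominators. They reproduce:

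- Superiority, normal formula: (1.960 + 0.842)² × (0.18²/2 + 0.108²) / 0.11² = 18.07 passive and 36.15 Ekso. A noncentral t at 38 and 19 gives 80.5% power.
- Non-inferiority, normal formula: (1.645 + 0.842)² × (0.18² + 0.108²) / (0.055 + 0.032)² = 35.99 per group. A noncentral t at 37 per group gives 80.2%.

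**What happens to each type of participant who attends both visits, if change in seconds is analysed**

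| Baseline | Week 12 | Change score | When the excluding fact arises |
|---|---|---|---|
| able | able | yes | not excluded |
| unable | able | none | before training |
| unable | unable | none | before training |
| able | unable | none; under exploratory LOCF an earlier time is kept | after training starts |

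The second and third rows are removed by a fact fixed before training, which randomisation balances in expectation. The loss is of information and of breadth of population. Only the fourth row is selected by what happened after training started.

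The documents do not say that the TUG is analysed as a change. If times at each visit are compared instead, the second row enters at week 12 only because those participants gained the ability, and the fourth row leaves. Both movements then depend on the outcome. LOCF cannot supply a value to anyone with no earlier time.

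**Size, under assumed shares.** Let u be the share unable at baseline, taken as 10% to 60%.

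- Participants with a change score = n × (1 − u), before any later loss of ability.
  - Trained arm: 38 × 0.90 = 34.2 down to 38 × 0.40 = 15.2.
  - Passive control: 19 × 0.90 = 17.1 down to 19 × 0.40 = 7.6.
- Newly able but uncounted, if one in four of the unable gains the ability = 0.25 × u × 38. This runs from 0.25 × 0.10 × 38 = 0.95 to 0.25 × 0.60 × 38 = 5.7 per trained arm.
- Lost because of outcome, if 5% of the able lose the ability = 0.05 × (1 − u) × 38. This runs from 0.05 × 0.90 × 38 = 1.7 to 0.05 × 0.40 × 38 = 0.8 per trained arm.

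The shares u, one in four and 5% are all assumptions.

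**The case against.** The strongest reply is that most of those dropped were unable before training, so leaving them out does not set unlike groups against each other. That stands. A reader might infer that the whole analysed set is selected after randomisation; the documents support that only for those who lose the ability or, if visit values are compared, also for those who gain it.

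A reader might also infer that the TUG result must understate a true difference. That would require the omitted participants to have a larger effect than those analysed. If able participants respond more, the completers would overstate the effect in the full population. Nothing in the documents settles this.

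Nor do the entry criteria show that everyone who meets them at the limit fails the TUG. Inclusion 7 is a ceiling and concerns safety and balance, exclusion 20 concerns safe transfer, and standby guarding could satisfy both. They show that some participants may be unable. Appendix A points the same way for the Berg scale, where it foresees people who can do none of the standing tasks.

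It is also fair to say that the case report form is not among the documents and may already have such an entry, that section 18.1 does not say whether a failed test counts as missing, and that losses of ability may be few in a population described as stable and chronic. WISCI-II, SCIM-III mobility and the Berg scale should capture some of the same changes. These points limit the consequence. They do not supply the missing rule, and the rank analysis in SAP section 1.1 does not either, because it ranks only observed values unless inability is given a rank.

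**Conclusion.** The point holds as a gap in the handling of one secondary endpoint. Followed as written, the plan gives no TUG value to a participant who attends and cannot do the test unaided.

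For those unable at baseline the cost is lost information and a narrower population: about 4 to 23 of 38 per trained arm without a change score (38 − 34.2 to 38 − 15.2), including about 1 to 6 newly able participants whose gain goes uncounted. For those who lose the ability after training starts, the exclusion depends on the outcome, so the comparison is not fully intent-to-treat; at an assumed 5% loss this is about 1 to 2 per trained arm.

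These counts rest on assumed shares. The direction of any bias is not established. The primary 10-metre walk analysis is unaffected, and no sample size or success criterion depends on the TUG. The point should be fixed, but it does not threaten the main conclusion.

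**What to change.** In Appendix A and section 18.1, with matching text in the SAP:

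1. At baseline and each evaluation, record 'unable to perform unaided' separately from 'visit missed'.
2. Compare arms at each visit with a rank analysis in which unable takes the worst rank, adjusting for or stratifying by ability at baseline. Those who gain or lose the ability then count in the right direction.
3. Do not carry an earlier time forward for a participant who is unable at an attended visit.
4. Report the number unable by arm and visit, and give seconds descriptively among completers.

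Settle the rule before unblinded data are seen, so that the choice is not driven by the results. The cost is one code on the case report form and a few lines of text, with no added procedure. The drawback is that rank units are less familiar than seconds. Scoring a rate with zero for unable is another option, but it may put many values at zero, which suits the planned analysis of variance poorly; ranks fit a method the SAP already names.
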